2.5 Benefit-Risk Assessment

The known potential risks to study participants associated with ISIS 416858 are elaborated on in the Guidance to Investigator section of the Investigator's Brochure. Additional study associated potential safety considerations include thrombocytopenia and increased major or CRNMB, which will be monitored closely.

Thrombocytopenia is a potential safety consideration based on preclinical GLP studies of ISIS 416858 in monkeys in which 4 of 32 monkeys in the > 10 mg/kg/wk dose groups developed severe thrombocytopenia ($< 50,000/\text{mm}^3$). Grade 4 ($< 25,000/\text{mm}^3$) thrombocytopenia has also been observed clinically with 2 other second generation ASOs in 2 different rare disease populations within the same chemical class as ISIS 416858 at doses > 200 mg/wk. If platelet count is $\leq 100,000/\text{mm}^3$, then weekly monitoring will be implemented (see [Section 8.5.2](#)). In the event of a platelet count $< 75,000/\text{mm}^3$, additional laboratory investigations will be conducted (see [Section 8.5.2](#)). Short-term steroid use will be recommended if platelet count $< 50,000/\text{mm}^3$. This is based on data from other programs at Ionis demonstrating that short-term steroid use improves recovery from thrombocytopenia. Additionally, no dose of Study Dmg will be administered before reviewing a valid platelet result. Valid platelet counts must be conducted every 2 weeks and reviewed prior to dosing. If the platelet result is unavailable (e.g., due to

hemolysis, clumping, etc.) from the central lab, a repeat local lab will be conducted and reviewed prior to dosing.

Increased major or CRNMB is also a potential safety consideration given the antithrombosis effects of ISIS 416858 investigated in this study. Clinical findings in Hemophilia C patients have demonstrated increased bleeding in the complete absence of FXI activity (seen mostly in high fibrinolytic tissues and at absolute FXI concentrations < 0.3 U/mL). However, increased major or CRNMB has not been observed to date with ISIS 416858 in the clinic or in preclinical studies. If bleeding were to occur, it can be rapidly reversed with infusion of plasma-derived FXI concentrate (Zhang et al. 2010) as well as specific FXI antidote (where available). Specific instructions for its use will be provided to site staff.

Based on the experience from previous clinical studies, it is anticipated that study subjects may benefit (anticoagulation) during the study although long term benefit cannot be assessed due to relatively short duration of the study.

3. EXPERIMENTAL PLAN

3.1 Study Design

This is a Phase 2 multicenter, double-blind, randomized, stratified, placebo-controlled study in ESRD subjects receiving hemodialysis at least 3 times per week for a minimum of 9 hours per week. Subjects will be stratified based on the diagnosis of documented atrial fibrillation (AF) at Screening (Yes/No), and then subjects will be randomized to 1 of 3 dose cohorts in a 1:1:1 ratio (Cohort A, Cohort B, and Cohort C). Additionally, subjects will be stratified by participation in the substudies. Within each dose cohort, subjects will be randomized in a 3:1 ratio to receive SC treatment with either ISIS 416858 or placebo (See [Study Design and Treatment Schema](#)). All standard of care hemodialysis therapies as prescribed by their providers, including heparins, will be continued.

Cohort A: 200 mg ISIS 416858 or placebo SC (3:1)
Cohort B: 250 mg ISIS 416858 or placebo SC (3:1)
Cohort C: 300 mg ISIS 416858 or placebo SC (3:1)

All cohorts will consist of up to 4-week screening period for procedures and a 26-week treatment period followed by a 12-week post-treatment evaluation period.

The SC Tolerability assessments using 0.9% sterile saline should be administered as 2 noncontiguous injections during the screening period on Study Days S-14 (\pm 3) and S-7 (\pm 3). Enrolled subjects will receive a SC dose of Study Drug (200 mg, 250 mg, or 300 mg ISIS 416858, or placebo) approximately weekly from Week 1 (Day 1) through Week 26.

The windows for study visits are specified in the Schedule of Procedures ([Appendix A](#)); please note that the Study Drug (ISIS 416858 or placebo) dose may not be administered more than once on the same day. Any questions on study procedures and visit windows may be directed to the Sponsor (or designee).

3.1.1 *Platelet Function/Activation Subgroup*

fu a subgroup of approximately 12 subjects in each cohort, platelet function and/or activation will be assessed. These subjects must have platelet counts that are $180,000/\text{mm}^3$ at Screening and who are not taking any anticoagulants or antiplatelet agents (other than aspirin).

At regularly scheduled visits during Weeks 1 (pre-dose), 12, 26, and 38, additional blood samples will be collected and processed for platelet function and/or activation tests as shown in [Appendix A](#).

3.1.2 *Pharmacokinetic Subgroup*

fu a subgroup of approximately 12 subjects in each cohort, additional Oto 24-hour PK sampling will be conducted following the first (Day 1, Week 1) and last dose (Day 176, Week 26) in order to determine the plasma PK parameters of ISIS 416858 in ESRD subjects, e.g., peak maximum concentration (C_{max}) and total plasma exposure (AUCo-t and AUC0-16shr), as well as clearance at steady-state (CL_{ssIF}). Subjects in this subgroup will have additional visits to the clinic to collect blood after dosing on Day 1, including a 24-hour (Day 2), and post-dose blood draw after Day 176 dose (Week 26) at 24-hours (Day 177), 48-hour (Day 178), and 7 days (Day 183). fu the event that dialysis is performed on these days, the blood draw should occur pre-dialysis. For more details of PK sampling schedule, see [Appendix C](#).

Subjects in the platelet function/activation subgroup may also participate in the PK subgroup and may withdraw consent for the subgroup specific procedures (e.g., blood draws for PK) without being withdrawn from dosing or from the study. If a subject withdraws consent from the subgroup procedures, he/she should remain on study and continue to follow all the non-subgroup assessments and procedures as outlined in [Appendix A](#).

3.2 Number of Study Centers

This study will be conducted at multiple centers worldwide.

3.3 Number of Subjects

Approximately 204 subjects are planned to be enrolled in parallel in this study and randomized equally across Cohorts A, B, and C.

The 3 multiple-dose cohorts are designed to assess the safety, tolerability, PK/PD of ISIS 416858. The sample size has been selected to ensure that the PK/PD, safety, and tolerability of ISIS 416858 will be adequately assessed while minimizing unnecessary subject exposure.

3.4 Overall Study Duration and Follow-up

For all cohorts, the Study will consist of a 4-week screening period for procedures after the informed consent is signed. An additional 21 days is permitted prior to screening period for signing of the informed consent. All cohorts will consist of a 26-week Treatment Period, and a 12-week Post-Treatment Evaluation Period. For all cohorts, please refer to the Schedule of Procedures in [Appendix A](#).

Subjects may be required to attend additional visits for monitoring of adverse events (AE) or abnormal investigation results. The frequency of additional monitoring will be determined by the Investigator in consultation with the Sponsor.

If Study Drug is discontinued for any reason, subjects are encouraged to continue their regular assessments for the duration of the treatment period and post-treatment evaluation period, unless subject informed consent is withdrawn.

3.4.1 *Screening*

After signing the informed consent form, subject eligibility for the study will be determined within 4 weeks prior to Study Day 1.

During the screening period, at Study Days S-14 (\pm 3) and S-7 (\pm 3), subjects should receive 2 noncontiguous SC injections of 0.75 mL saline. As with Study Drug, these may be administered immediately after dialysis is completed when blood is returning to the subject but must be within 2 hours after dialysis (within 15 minutes is preferred) to determine tolerability to SC injections.

All women will have a serum pregnancy test done between Study Days S-28 and S-14 that must be resulted prior to dosing on Study Day 1.

All screening lab re-tests should be resulted by the central lab prior to randomization on Study Day 1.

3.4.2 *Treatment*

Eligible subjects will receive study treatment every week for 26 weeks. The treatment period consists of the period from the first Study Drug (ISIS 416858 or placebo) injection to the last injection on Day 176 (Week 26), or early study termination.

3.4.3 *Post-Treatment*

Subjects will have follow-up evaluation visits on Study Week 27 (PK Subgroup only), and for Study Weeks 28, 30, 32, 34, 36, 38 (all subjects), or early study termination. The final study visit will be Study Day 260.

3.5 End-of-Study

The End-of-Study is defined when the last subject has had their last visit.

4. SUBJECT ENROLLMENT

4.1 Screening

Before subjects may be enrolled into the Study, the Sponsor or designated contract research organization (CRO) requires a copy of the Study Center's written institutional review board (IRB) approval of the protocol, informed consent form, and all other patient information and/or recruitment material.

Subjects must sign the consent form before any screening tests or assessments are performed, this can be done up to 49 days prior to randomization. At the time of consent, the patient will be

considered enrolled into the Study and will be assigned a unique screening number before any study procedures, including screening procedures, are performed.

Screening labs must be perf01med within 28 days before Study Day 1. If screening labs are to be perf01med outside of this window, then additional samples should normally be drawn prior to Study Day 1 to ensure that labs still fulfill the eligibility criteria. A single re-test of abn01mal screening labs may be done at the central lab to evaluate subject eligibility.

During the screening period, at Study Day S-14 (± 3) and S-7 (± 3), subjects should receive 2 noncontiguous SC injections of 0.75 mL saline as described in [Section 3.4.1](#).

At the time of randomization, subjects will be assigned a unique subject identification number. This number will be used to identify the subject throughout the trial and must be used on all study documentation related to that subject. The screening number and subject identification number must remain constant throughout the entire trial. In the event the subject is re-consented and re-screened, the subject must be given a new screening number. Screening numbers and subject identification numbers, once assigned, will not be re-used.

4.2 Randomization

Subjects will be randomized on Study Day 1 after all screening assessments have been completed and after the Investigator has verified that they are eligible per criteria in [Sections 5.1](#) and [5.2](#). No subject may begin treatment prior to randomization and assignment of a unique subject identification number.

All subjects will be randomized using an automated system (IXRS). Subjects will be stratified based on the diagnosis of documented AF at Screening (Yes/No). Additionally, subjects will be stratified by participation in the substudies. Then, subjects will be randomized in parallel to 1 of 3 dose cohorts in a 1:1:1 ratio (Coh01i A, Coh01t B, and Coh01t C). Within each dose cohort, subjects will be randomized in a 3:1 ratio to receive SC treatment with either ISIS 416858 or placebo.

4.3 Unblinding of Treatment Assignment

The Sponsor and all subjects, monitors, and Study Center personnel related to the Study, will be blinded throughout the Study. However, if a subject has suffered a Serious Adverse Event (as defined in [Section 9.3.3](#)), and/or when knowledge of the treatment assignment will impact the clinical management of the subject, the Investigator will have the ability to unblind the treatment assignment for that subject using the automated system. The Sponsor or designee must be inf01med of the unblinding of a subject within 24 hours. All SUSARs will be unblinded by the Sponsor or designee for the purpose of regula01y rep01ting (see [Section 9.2](#)).

Every reasonable attempt should be made to complete the early termination study procedures and observations (see [Appendices A](#) and [B](#)) prior to unblinding, as knowledge of the treatment ai·m could influence subject assessment.

In addition, the safety team assigned to review relevant Study Drng safety and tolerability data during the study in a blinded fashion will also have the ability to request the Ionis Drng Safety

Oversight Committee, chaired by the Chief Medical Officer, for unblinding the treatment assignment if needed for safety and data interpretation.

During the study, an unblinded interim analysis may be conducted to assess the safety and PK/PD results. The analysis will be executed with controlled dissemination of data to ensure the integrity of ongoing data collection while maintaining sufficient blinding in the study. Details of these controls will be described in the Statistical Analysis Plan (SAP).

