2.2 Therapeutic Rationale

Approximately 2 million individuals receive dialysis for end-stage renal disease (ESRD) globally and this number is increasing rapidly as both the incidence of ESRD rises and access to dialysis as a life sustaining therapy increases (Caskey et al. 2011). Dialysis patients are at high risk of thrombotic events due to their high degree of comorbid conditions and because they have a hypercoagulable state. This hypercoagulable state appears to be driven by widely used drugs (e.g., erythropoiesis stimulating agents), inflammation and endothelial dysfunction from uremia, and contact between blood and the extracorporeal circuit. The hypercoagulable state results in clinically meaningful negative outcomes. The risk of stroke in dialysis patients may be 10-times higher than the general population (Sood et al. 2009). Dialysis patients have a 5-fold higher risk of myocardial infarction than the general population and even moderate chronic kidney disease alone is considered the risk equivalent of diabetes mellitus for cardiovascular thrombotic events (Go et al. 2004; Tonelli et al. 2012). Furthermore, dialysis patients depend on patent vascular access to receive hemodialysis. Dialysis patients have a high chance, approximately 10% chance per year of having their vascular access compromised by thrombosis resulting in a potentially life-threatening situation requiring urgent intervention (Jean-Baptiste et al. 2008; Schild et al. 2008). Finally, dialysis patients are hospitalized an average of 3 times per year and are at high risk of VTE (Tveit et al. 2002). Despite this high risk of VTE, there remains considerable uncertainty as to the benefit-to-risk ratio of VTE prophylaxis. This is of particular importance when considering the optimal treatment for ESRD, renal transplantation, in which VTE can compromise the ability to receive a transplant, the function of an already transplanted kidney,

and/or the life expectancy of a patient who recently received a transplant (i.e., post-operative VTE) (Irish 2004).

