8.7 Discontinuation of Study Drug

A subject must permanently discontinue Study Drug (ISIS 416858 or placebo) for any of the following:

- The subject becomes pregnant. Report the pregnancy according to instructions in [Section 9.5.4](#)
- The subject withdraws consent
- The subject experiences an AE that necessitates permanent discontinuation of Study Drug
- The subject develops laboratory test abnormalities that meet any of the stopping rules listed in [Sections 8.6.1 to 8.6.3](#)
- The subject experiences an AE that necessitates unblinding of the Investigator to the subject's treatment assignment
- The subject is no longer on maintenance hemodialysis of at least 3-times per week for a minimum of 9 hours per week which includes a change in dialysis modality or renal transplantation
- The subject begins treatment with a disallowed concomitant medication as described in [Section 8.9.1](#)

The reason for discontinuation of Study Drug must be recorded in the electronic Case Report Form (eCRF) and source documentation. Every effort should be made to complete the early termination study procedures and observations as detailed in [Appendix A](#) at the time of withdrawal.

Subjects who discontinue Study Drug are encouraged to remain in the study. Subjects that discontinue treatment such as in cases where hemodialysis is held for > 2 weeks or stopped, or there is a change of dialysis modality (i.e., hemodialysis to peritoneal dialysis) or receive a renal transplant (See [Section 6.2.2](#)) are encouraged to complete the treatment and the post-treatment evaluation period visits unless consent is withdrawn.

If the subject declines or is unable to participate in the post-treatment evaluation period, the investigator should clarify what type of follow-up the subject is agreeable to, such as by telephone or through their treating physicians. At the very least, the subject's status at the end of the protocol defined study period should be ascertained and documented wherever possible. The agreed means of follow-up should be documented in the subject's records and notified to the Sponsor.

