9.3 Definitions

9.3.1 *Adverse Event*

An adverse event (AE) can be any unfavorable and unintended sign (including an abnormal laboratory finding), symptom, or disease temporally associated with the use of a medicinal (investigational) product, whether or not the AE is considered related to the medicinal (investigational) product.

Adverse events are to be identified between study visits by evaluating components of the medical record that contain valid and verifiable claims about a medically untoward event. For hemodialysis subjects, this includes a complete review of changes in the dialysis prescription in the dialysis chart orders section or information provided to the study staff directly by the subject. Dialysis treatment summaries (rnn-sheets) should be reviewed for pertinent information when indicated.

9.3.2 *Adverse Drug Reaction and Unexpected Adverse Drug Reaction*

All noxious and unintended responses to a medicinal product related to any dose should be considered adverse drug reactions (ADR).

An unexpected ADR is any ADR, the nature or severity of which is not consistent with the applicable product information, e.g., Investigator's Brochure for an unapproved medicinal (investigational) product.

9.3.3 *Serious Adverse Event (SAE)*

A SAE is any AE that in the view of either the Investigator or Sponsor, meets any of the following criteria:

- Results in death
- Is life threatening: that is, poses an immediate risk of death at the time of the event
An AE or suspected adverse reaction is considered "life-threatening" if, in the view of either the Investigator or Sponsor, its occurrence places the subject at immediate risk of death. It does not include an AE or suspected adverse reaction that, had it occurred in a more severe form, might have caused death
- Requires inpatient hospitalization or prolongation of existing hospitalization
Hospitalization is defined as an admission of greater than 24 hours to a medical facility and does not always qualify as an AE
- Results in a persistent or significant incapacity or substantial disruption of the ability to conduct normal life functions

- Results in a congenital anomaly or birth defect in the offspring of the subject (whether the subject is male or female)

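### Section 4.3 lets the investigator break the blind after any SAE, even when the assignment has no bearing on care

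*Combined protocol and SAP*

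**What the plan says.** Section 4.3 starts from blinding throughout the study and then makes an exception with two triggers. The first is "However, if a subject has suffered a Serious Adverse Event". The second follows directly: "and/or when knowledge of the treatment assignment will impact the clinical management of the subject, the Investigator will have the ability to unblind" the assignment in the automated system. The sponsor must be told within 24 hours. The same section asks sites to try to complete the early termination assessments before unblinding, and gives as its reason that knowing the arm could affect how the subject is assessed.

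Section 9.3.3 lists among the SAE criteria: "Requires inpatient hospitalization or prolongation of existing hospitalization". It counts only admissions of more than 24 hours and adds that an admission is not always an adverse event. Section 2.2 states that "dialysis patients are hospitalized an average of 3 times per year". Section 3.4.2 sets the exposure: "Eligible subjects will receive study treatment every week for 26 weeks".

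Section 8.7 lists among the reasons for permanently stopping study drug: "The subject experiences an AE that necessitates unblinding of the Investigator to the subject's treatment assignment".

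Section 10.1.1 and SAP Section 1.3.1 make MB plus CRNMB in the treatment period the primary safety outcome. Section 8.5.3 defines CRNMB by example. Section 8.6.3 describes MB and CRNMB as assessed by the investigator. Neither document describes a blinded adjudication committee.

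**The concern.** An emergency code break normally needs a clinical reason. Here the first trigger has none: an admission for pneumonia would entitle the investigator to open the code although the answer could not alter treatment. SAEs are common in dialysis patients, so the permission is not confined to rare emergencies.

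Subjects are encouraged to stay in the study after stopping drug (Sections 8.6 and 8.7), so an investigator who has seen the assignment may go on assessing that subject. CRNMB leaves room for judgment, because its definition turns on consequences such as an examination or an intervention. The investigator also records relatedness (Section 9.4.3). If an unblinded investigator leans one way on borderline bleeds, the comparison of bleeding incidence between arms can shift.

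The wording also fits poorly with the rest of the protocol. Section 8.7 covers unblinding that an adverse event makes necessary and does not clearly say what follows an optional code break after an SAE. Section 9.2 has the sponsor send SUSARs to investigators in blinded form, whereas 4.3 lets an investigator open the code after any SAE.

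**Working it through.** The documents give no expected number of unblindings and no expected SAE proportion, so there is no stated figure to reproduce. The check has three parts.

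**1. Is an SAE alone sufficient?** Two conditions joined by and/or are met when either one is met. The effect-on-management condition belongs to the second trigger only. Read literally, an SAE alone is enough.

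**2. How many subjects could become eligible during treatment?**

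Inputs from the protocol:
- mean hospitalization rate 3 per year (Section 2.2)
- exposure 26 weeks, or 26/52 = 0.5 year (Section 3.4.2)
- planned sample about 204 (Section 3.3)

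Assumptions, not in the documents:
- s, the share of admissions that are SAEs: 25% to 100%
- the distribution of admissions over subjects: Poisson (no clustering), or negative binomial with dispersion k, where a smaller k means that admissions cluster in fewer subjects

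Formulas: μ = 3 × 0.5 × s. The share with at least one qualifying admission is 1 − exp(−μ) for Poisson and 1 − (1 + μ/k)^(−k) for negative binomial.

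| s | μ | Poisson | k = 1 | k = 0.5 |
|---|---|---|---|---|
| 100% | 1.500 | 77.7% | 60.0% | 50.0% |
| 75% | 1.125 | 67.5% | 52.9% | 44.5% |
| 50% | 0.750 | 52.8% | 42.9% | 36.8% |
| 25% | 0.375 | 31.3% | 27.3% | 24.4% |

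Top corner: 1 − exp(−1.5) = 0.777, and 204 × 0.777 ≈ 158 subjects. Bottom corner: 1 − (1.75)^(−0.5) = 0.244, and 204 × 0.244 ≈ 50 subjects. Counting to Day 176 instead changes little: μ = 3 × 176/365.25 = 1.446 with every admission counted, and Poisson gives 76.4%. Stronger clustering lowers the floor slightly: k = 0.3 with s = 25% gives 21.6%. SAEs without an admission would raise every figure.

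**3. How much treatment time could be affected?** Only time after a qualifying event matters. If the code were opened at the first qualifying admission, the expected share of the 26 weeks that follows it is:
- Poisson, s = 100%: 1 − 0.777/1.5 = 48%
- k = 1, s = 100%: 1 − ln(2.5)/1.5 = 39%
- k = 0.5, s = 25%: 1 − (√1.75 − 1)/0.375 = 14%

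These are ceilings, because they assume that every permitted code break takes place.

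**The case against.** A reader might infer that most of the trial would be unblinded, or that the primary outcome is compromised. The documents do not support either reading.

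- **The rate is not a trial rate.** Three a year is a mean for dialysis patients in general. Section 5.2 excludes recent major events, recent major surgery and patients whose nephrologist would not be surprised by death within a year. Short admissions do not count (9.3.3), documented elective admissions are not SAEs (9.5.2), and events typical of ESRD are not adverse events unless atypical or possibly drug-related (9.4). The 78% needs every admission to be an SAE and no clustering. This stands, and it is why only a range can be given.
- **Permission is not unblinding.** No unblinding rate is given. The 24-hour notice and the request for assessments beforehand both discourage it. This stands.
- **Bleeding SAEs are mostly counted already.** A reader might infer that code breaks after a bleed contaminate the primary outcome most. But an overt bleed leading to admission would ordinarily be at least CRNMB in either arm, and SAP Section 2.3.3.3 counts subjects with either type, so later bleeds in that subject add nothing. MB also rests largely on concrete criteria. This stands. The remaining path is a non-bleeding SAE, an actual code break, then a borderline bleed.
- **Relatedness has a second reader.** Under Section 9.2 the sponsor assesses causality of all reported SAEs independently. This stands for SAEs but would not reach a non-serious CRNMB.
- **The analysis is descriptive.** SAP Section 2.3.3.3 specifies incidence and a Kaplan-Meier display of first MB, with no test of MB plus CRNMB. This limits the consequence but does not remove it, since this is the primary safety result.
- **The investigator's role is partly inferred.** The reference to investigator assessment sits in the dosing-stop rule (8.6.3). That the same call is final for the analysis is likely but not stated.

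SAP Section 2.1.4 says that investigators remain blinded throughout. That sentence concerns the interim analysis, so it should not be pressed as a contradiction of individual code breaks.

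**Conclusion.** The point holds as a defect in a stated rule with limited consequences. Section 4.3 allows a code break after any SAE without a clinical reason, and that is looser than the necessity test in Section 8.7.

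An illustrative 24% to 78% of subjects, about 50 to 158 of 204, could become eligible during treatment. The range rests on the cited general rate of 3 a year, an SAE share of 25% to 100%, and clustering from none to k = 0.5. It measures eligibility; the documents do not allow an estimate of actual unblinding or of bias.

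What is exposed is mainly the classification of borderline bleeds after an earlier, usually non-bleeding, SAE, and the investigator's relatedness call, most of all for non-serious CRNMB. The present safeguard does not close this gap. It asks for assessments before unblinding but does not require bleed class or relatedness to be recorded first, and it cannot protect bleeds that come later. The change is worth making because it costs almost nothing.

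**What to change.** In Section 4.3, remove the stand-alone SAE trigger. Suggested sense: *the investigator may open the code for a subject only if knowing the assignment will affect how that subject is managed, for example after an SAE.* An SAE whose care depends on the assignment still qualifies.

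Reconcile 4.3 with 8.7, so that it is clear how the discontinuation rule applies to each kind of code break that 4.3 permits. How study drug should be handled after a code break is for the sponsor to state.

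Where the emergency allows, have the investigator enter the MB/CRNMB classification and relatedness of any bleed in the eCRF before the code is opened, and log the reason for opening it in the IXRS.

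Cost: a sentence or two in 4.3, one IXRS field, and slightly less investigator discretion. Access needed for patient care is unchanged.
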